#### 7.9.4 Safety Analysis

The total number of AEs, and the total number of subjects experiencing an AE will be presented by Classification from the Investigator and the AEMB as per the tables below. 

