10. STUDY DESIGN

10.1 STUDY DESIGN

This is a retrospective, multi-center, case series study to collect clinical data that will evaluate post-market Safety and Performance of the Q-Fix™ All- Suture Anchor System in the knee, shoulder and hip.

CONFIDENTIAL AND PROPRIETARY

This document contains information that is confidential and proprietary to Smith & Nephew PLC and Smith & Nephew, Inc. and is intended for use only by Smith & Nephew and its manufacturer. It shall not be reproduced or copied in whole or in part, nor shall the contents be disclosed by any means without prior written permission from Smith & Nephew, nor shall anyone make any use of it that is contrary to the expressed or implied wishes of Smith & Nephew.

Study Protocol—Device	
Safety and Performance of Q-Fix™ All-Suture Anchor System	Number: 17-5010-11
	Version: 2.0 05SEP2019
	Page: Page 23 of 62

A minimum of 90 subjects and a maximum of 450 subjects in the United States who underwent surgery in the knee, shoulder or hip using the Q-Fix™ All- Suture Anchor System are planned to be enrolled into the study after the fulfilment of all inclusion and exclusion criteria.

Data from eligible subjects will have their data recorded on case report forms.

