12.4 SAFETY ANALYSES

All safety analyses will be conducted using the safety population. The number of incidences and number of subjects reporting all adverse events will be summarized both overall and by seriousness, severity,

CONFIDENTIAL AND PROPRIETARY

This document contains information that is confidential and proprietary to Smith & Nephew PLC and Smith & Nephew, Inc. and is intended for use only by Smith & Nephew and its manufacturer. It shall not be reproduced or copied in whole or in part, nor shall the contents be disclosed by any means without prior written permission from Smith & Nephew, nor shall anyone make any use of it that is contrary to the expressed or implied wishes of Smith & Nephew.

Study Protocol—Device	
Safety and Performance of Q-Fix™ All-Suture Anchor System	Number: 17-5010-11
	Version: 2.0 05SEP2019
	Page: Page 31 of 62

relationship to study device and outcome. Incidences and number of subjects reporting device deficiencies will also be summarized. Further summaries of safety data may be described in the SAP.

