23.3 PROTOCOL AMENDMENT #1

- **General Purpose**

The purpose for this amendment is to:

- 1) Decrease age limit to ≥ 13 years to include adolescents as it was determined that the Q-Fix™ anchor is being used by sites in adolescents; it is important to obtain information on the safety and performance in the adolescent population as well as in adults. A secondary objective is added so that an analysis may be done on adolescents and young adults ages 13-21 years of age. As this retrospective study is granted a waiver of informed consent for adults, it is requested for adolescents as well.
- 2) Increase enrollment maximum to 450 subjects to allow for the enrollment of adolescents and additional Q-Fix™ MINI subjects (150 maximum per joint type.)
- 3) Revise the timeline to account for the enrollment of adolescents; this amendment is not expected to affect the overall study duration.
- 4) Include both open and arthroscopic surgeries in the study as it was determined that sites used the Q-Fix™ anchor in both arthroscopic and open soft tissue repair surgeries; it is important to obtain safety and performance data for both types of surgery. Also clarified that as the study is collecting real world safety data, use in knee, shoulder, and hip may be collected beyond the indications for use.
- 5) Clarify that another enrollment date may be used if agreed upon by Investigators and site, as long as a bias is not introduced using this date. In addition, the enrollment start date for Q-Fix™ MINI may be different than the start date for the 1.8 and 2.8mm Q-Fix™ anchors to ensure that the data is collected on all 3 sizes of the Q-Fix™ anchor.

- **Rationale**

The rationale for the changes is as follows:

- 1) From the screening and enrollment logs provided by the sites to the Sponsor, individuals <18 years old are receiving Q-Fix™ anchors, but this population is not included per the current

CONFIDENTIAL AND PROPRIETARY

This document contains information that is confidential and proprietary to Smith & Nephew PLC and Smith & Nephew, Inc. and is intended for use only by Smith & Nephew and its manufacturer. It shall not be reproduced or copied in whole or in part, nor shall the contents be disclosed by any means without prior written permission from Smith & Nephew, nor shall anyone make any use of it that is contrary to the expressed or implied wishes of Smith & Nephew.

Study Protocol—Device	
Safety and Performance of Q-Fix™ All-Suture Anchor System	Number: 17-5010-11

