#### 4. Study Objectives

##### 4.1 Primary Objective

The purpose of this study is to demonstrate the safety and performance of the Q-Fix® All-Suture Anchor System in hip, shoulder and knee repair.

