##### 5.3 Safety Endpoints

- Adverse events, to be evaluated by type, frequency, severity an relatedness to the study treatment
- Device-related re-intervention
- All adverse events (AEs) occurring from the time of surgery until revision or study completion
- Device related AE and SAE's

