## 7.9 Evaluation of Efficacy

### 7.9.1 Analysis of Primary Endpoint

- Overall clinical success rate at 6 months will be summarized using count (n) and percentage (%). A 95% Confidence Interval (CI) for the percentage of subjects with clinical success at 6 months will be computed using exact methods. This same analysis will be repeated by the position, i.e. the hip, shoulder and knee will be reported. These analyses will be carried out using the per protocol population as the primary analysis population with the safety population used for sensitivity analyses.

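### Adverse events and device deficiencies are summarised only across joints, although re-intervention is reported by joint, and no outcome is reported by open versus arthroscopic repair

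*SAP*

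**What the plan says.** **Adverse events.** SAP 7.9.4 states: "The total number of AEs, and the total number of subjects experiencing an AE will be presented by Classification". The two table layouts there cross seriousness with device-relatedness and anticipation. Their cells hold a device placeholder, a count and a percentage, with no joint dimension. The AE listing described after them does not name joint or approach either. Protocol 12.4 states: "The number of incidences and number of subjects reporting all adverse events will be summarized both overall and by seriousness, severity", then adds relationship to device and outcome, plus a summary of device deficiencies. It leaves further safety summaries to the SAP, which adds none by joint or approach.

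**Joints.** SAP 4.1 gives the purpose as showing safety and performance of the "All-Suture Anchor System in hip, shoulder and knee repair". Protocol 10.1 likewise refers to the "All- Suture Anchor System in the knee, shoulder and hip". For the primary endpoint SAP 7.9.1 says: "This same analysis will be repeated by the position, i.e. the hip, shoulder and knee will be reported". SAP 7.9.2 applies the same analysis at 12 months. It also tabulates "Device-related re-intervention", a safety endpoint under SAP 5.3, for the whole sample and by indication; the sample-size text uses indication to mean shoulder, hip or knee.

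**Surgical approach.** Protocol 23.3 (Amendment 1, General Purpose, item 4) explains the admission of open repair: "it is important to obtain safety and performance data for both types of surgery". Protocol 12.2 defines the Safety Population to cover arthroscopic or open repair. SAP 3 and SAP 7.2 mention arthroscopic repair only, although SAP 2 says the SAP is based on protocol version 2.0 and SAP 7.11 declares no changes.

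**The concern.** The study is organised by joint: enrolment minimums, clinical success and device-related re-intervention are all set or reported that way. AEs, device-related AEs and SAEs, and device deficiencies are the exception, and no reason is given. If knee repairs form a small part of the sample, a pooled AE percentage mainly describes hip and shoulder. A knee excess in events that do not lead to re-intervention would be hard to see.

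The approach question is similar. Open repairs were added in order to learn about them, but no planned table separates them. The SAP population wording, read literally, does not cover them at all.

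**Working it through.** **1. The plan's own sample-size figures.** Inputs from protocol 13 and SAP 6.1: 84 evaluable, 28 per joint, 5% loss, 95% success, precision within 11%.
- 84/(1 − 0.05) = 88.4, so 89; 28/(1 − 0.05) = 29.5, so 30 per joint, and 3 × 30 = 90. The stated 90 reproduces.
- Half-width of the exact (Clopper-Pearson) 95% interval at 95% success: 10.1% for n = 28 (11.3% if 26/28 succeed) and 5.3% for n = 84. The stated 11% therefore fits the per-joint number, not the pooled one. This concerns clinical success, but it shows that joint-level estimates were in view.

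**2. Which outcomes are split, and how.**

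| Outcome | By joint | By approach |
|---|---|---|
| Success at 6 and 12 months | Yes (SAP 7.9.1, 7.9.2) | No |
| Device-related re-intervention | Yes (protocol 12.3.2, SAP 7.9.2) | No |
| AEs, device-related AEs and SAEs | No (protocol 12.4, SAP 7.9.4) | No |
| Device deficiencies | No (protocol 12.4) | No |

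The other success subgroups are age 13–21 (SAP 7.9.2) and anchor size (SAP 7.9.3).

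**3. How far pooling can hide a knee excess.** Amendment 1 gives 106 hip, 99 shoulder and 24 knee: total 229, knee 24/229 = 10.5%. The AE rates below are assumptions, because the documents give none.
- 5% in hip and shoulder, 15% in knee: (205 × 0.05 + 24 × 0.15)/229 = 13.85/229 = 6.0%. A threefold knee rate moves the pooled figure by about one point.
- 3% in hip and shoulder, 15% in knee: (205 × 0.03 + 24 × 0.15)/229 = 9.75/229 = 4.3%.
- If the final split were equal, the first set of rates would pool to (5 + 5 + 15)/3 = 8.3%. The excess is then less diluted, but the table still would not show which joint it came from.

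**4. What zero events would support.** The upper exact 95% limit for 0/n is 1 − 0.025^(1/n).

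| n | Upper limit |
|---|---|
| 229 (pooled at Amendment 1) | 1.6% |
| 106 (hip) | 3.4% |
| 99 (shoulder) | 3.7% |
| 24 (knee at Amendment 1) | 14.2% |
| 30 (knee minimum) | 11.6% |
| 150 (maximum per joint) | 2.4% |

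**5. Approach.** The documents give no count of open repairs, so no size can be computed. For feasibility only, an assumed open share of 10% to 30% of 24 knees is 2.4 to 7.2 subjects. Zero events in 2 or in 7 gives upper limits of 84% or 41%, so rows by approach within joint could be uninformative.

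**The case against.** The case on the other side is substantial.

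- **Safety by joint is partly covered.** A reader might infer that safety by joint gets no answer. The documents do not support that. Device-related re-intervention is a listed safety endpoint and is tabulated by joint, and freedom from re-intervention is given by joint with exact intervals. A knee problem that led to re-intervention would show.
- **No comparison is promised.** Protocol 7.1 names no joints, and SAP 4.1 can be read as naming scope. The amendment text justifies including open cases. Where Amendment 1 wanted a separate analysis, for ages 13–21, it added an endpoint; it added none for approach. A split by approach is therefore a sensible request, not a broken commitment.
- **The joint counts are interim.** Twenty-four knees is below the protocol's own minimum of 30, and the maximum is 150. The 14.2% is not a forecast of the final position.
- **No AE interval is planned.** One might fear that a tight pooled interval would be read as applying to each joint. SAP 7.9.4 plans counts and percentages only, so the limits above show what the data could support, not what will be reported.
- **Approach may not be recorded.** SAP 7.5.3 lists the intervention among operative summaries but names no field for open versus arthroscopic, and Amendment 1 says the case report forms are unaffected.
- **The table shells are not available.** SAP 2 says they accompany the SAP, and they may contain further splits.

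All of this narrows the point. It does not remove it: neither document commits to AEs by joint or to any outcome by approach, and the mismatch in the SAP population wording is plain.

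**Conclusion.** The point holds in this limited form. AEs, device-related AEs and SAEs, and device deficiencies are summarised without a joint split, although the SAP objective names the three joints and the other main outcomes are reported by joint. No outcome is reported by approach, and SAP 3 and SAP 7.2 have not been brought into line with protocol 12.2.

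The size of the joint issue rests on the interim 106/99/24 split and on assumed AE rates: a threefold knee rate moves the pooled figure from 5% to 6.0%, and zero events would exclude rates above 1.6% pooled but only above 14.2% for 24 knees (11.6% for 30). No size can be given for approach.

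A reader might also infer from the SAP wording that open repairs will be left out of the analysis. The documents do not show that: the SAP says it follows protocol version 2.0 and declares no changes, so an incomplete update is the likelier explanation. The primary estimate is unaffected. This is a worthwhile descriptive addition, not a flaw in the main inference.

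**What to change.** 1. In SAP 7.9.4, repeat both AE classification tables by joint and include the device-deficiency summary from protocol 12.4 in the same layout. Give subject denominators, and exact 95% intervals for the proportions of subjects with device-related AEs and SAEs.
2. Align SAP 3 and the Safety Population in SAP 7.2 with protocol 12.2, so that both cover arthroscopic and open repair.
3. Confirm that approach is recorded on the case report form. If it is, add descriptive open and arthroscopic rows to the 6- and 12-month success tables and to the AE tables, overall rather than within joint where cells are very small.

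Items 1 and 2 cost SAP wording and repeat runs of tables already planned. Item 3 costs the same if approach is captured; otherwise it needs extra abstraction from the operative records. The downside is small cells with wide intervals. These should be presented as descriptive, without comparison between joints or approaches.

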#### Number of Adverse Events by Classification

ADVERSE EVENTS	NON DEVICE-RELATED	DEVICE-RELATED	
NON-SERIOUS	ADVERSE EVENT (AE)	ADVERSE DEVICE EFFECT (ADE)	
	<device>	<device>	
	<#> x%	<#> x%	
SERIOUS	SERIOUS ADVERSE EVENT (SAE)	SERIOUS ADVERSE DEVICE EFFECT	
		ANTICIPATED	UNANTICIPATED
		ANTICIPATED SERIOUS ADVERSE DEVICE EFFECT (ASADE)	UNANTICIPATED SERIOUS ADVERSE DEVICE EFFECT (USADE)
	<device>	<device>	<device>
	<#> x%	<#> x%	<#> x%

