10.2.3 Safety Endpoints

- Device-related re-intervention
- All adverse events (AEs) occurring from the time of surgery until revision or study completion
- Device related AEs and serious adverse events (SAE's)

CONFIDENTIAL AND PROPRIETARY

This document contains information that is confidential and proprietary to Smith & Nephew PLC and Smith & Nephew, Inc. and is intended for use only by Smith & Nephew and its manufacturer. It shall not be reproduced or copied in whole or in part, nor shall the contents be disclosed by any means without prior written permission from Smith & Nephew, nor shall anyone make any use of it that is contrary to the expressed or implied wishes of Smith & Nephew.

Study Protocol—Device	
Safety and Performance of Q-Fix™ All-Suture Anchor System	Number: 17-5010-11
	Version: 2.0 05SEP2019
	Page: Page 24 of 62

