14.1 DEFINITIONS

The categories of adverse events are shown in table 14.1-1. The definitions for each of these categories are given in the subsequent sections (see reference within the table).

Table 14.1-1: Categories of Adverse Event

	NOT DEVICE- RELATED	DEVICE- OR PROCEDURE-RELATED	
NON-SERIOUS	ADVERSE EVENT (AE) (SEE 14.1.1)	ADVERSE DEVICE EFFECT (ADE) (SEE 14.1.2)	
SERIOUS	SERIOUS ADVERSE EVENT (SAE) (SEE 14.1.3)	SERIOUS ADVERSE DEVICE EFFECT (SADE) (SEE 14.1.3)	
		ANTICIPATED	UNANTICIPATED
		ANTICIPATED SERIOUS ADVERSE DEVICE EFFECT (ASADE) (SEE 14.1.4)	UNANTICIPATED SERIOUS ADVERSE DEVICE EFFECT (USADE) (SEE 14.1.4)

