14.1.2 Adverse Device Effect

An ADE is an adverse event that, in the opinion of the Investigator, is related to the IP or the procedure.

Not Related - An AE is considered to be not related to the use of an IP or the procedure when the effect is DEFINITELY UNRELATED or UNLIKELY to have any relationship to the use of the IP or the procedure;

CONFIDENTIAL AND PROPRIETARY

This document contains information that is confidential and proprietary to Smith & Nephew PLC and Smith & Nephew, Inc. and is intended for use only by Smith & Nephew and its manufacturer. It shall not be reproduced or copied in whole or in part, nor shall the contents be disclosed by any means without prior written permission from Smith & Nephew, nor shall anyone make any use of it that is contrary to the expressed or implied wishes of Smith & Nephew.

Study Protocol—Device	
Safety and Performance of Q-Fix™ All-Suture Anchor System	Number: 17-5010-11
	Version: 2.0 05SEP2019
	Page: Page 33 of 62

Related – An AE is considered to be related to the use of an IP or the procedure when there is a POSSIBLE, PROBABLE, or DEFINITE relationship between the AE and the use of the IP or the procedure.

An ADE is further categorized depending on whether the criteria in section 14.1.3 and 14.1.4 are met.

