14.1.4 Anticipated/Unanticipated Serious Adverse Device Effect

CONFIDENTIAL AND PROPRIETARY

This document contains information that is confidential and proprietary to Smith & Nephew PLC and Smith & Nephew, Inc. and is intended for use only by Smith & Nephew and its manufacturer. It shall not be reproduced or copied in whole or in part, nor shall the contents be disclosed by any means without prior written permission from Smith & Nephew, nor shall anyone make any use of it that is contrary to the expressed or implied wishes of Smith & Nephew.

Study Protocol—Device	
Safety and Performance of Q-Fix™ All-Suture Anchor System	Number: 17-5010-11
	Version: 2.0 05SEP2019
	Page: Page 34 of 62

An USADE is a serious ADE that meets any of the above definitions but is also considered, by the Investigator, to be caused by or related to the IP, not previously identified in nature, severity or degree in the IFU.

An Anticipated Serious Adverse Device Effect (ASADE) is a serious ADE that does not meet the criteria for a USADE.

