#### **CONFIDENTIAL AND PROPRIETARY**

This document contains information that is confidential and proprietary to Smith & Nephew PLC and Smith & Nephew, Inc. and is intended for use only by Smith & Nephew and its manufacturer. It shall not be reproduced or copied in whole or in part, nor shall the contents be disclosed by any means without prior written permission from Smith & Nephew, nor shall anyone make any use of it that is contrary to the expressed or implied wishes of Smith & Nephew.

Statistical Analysis Plan	
Safety and Performance of Q-Fix ® All-Suture Anchor System	Number: 17-5010-11
	Version: 2.0, 23-Oct-2019
	Page: 14 of 20

End Date for SAE will be based on the AE Stop Date or Death Date as found in the Related AE.

When there is a Follow-up AE, the end date will come from the AE Stop Date or Death Date on the latest or highest numbered Follow-up AE.

Also, a check will be performed for all bilateral knee subjects to remove from the AE summaries the double entries referencing the same Adverse Event for a single implant twice. Where an AE CRF is filled out regarding the contralateral knee after an AE has already been reported for the ipsilateral knee.

An ADE is defined as an Adverse Event that is Possibly or Probably Related to Device or Procedure.

The Expectation variable on the AE CRF is only to be filled out for Serious ADEs.

All Adverse Events will be assessed by the Investigator to determine relatedness and severity. The AEMB may subsequently classify events into SAEs, ADEs, SADEs, UADEs, USADEs etc. All safety Tables will presented based on the Investigator's and/or AEMB classifications.

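### SAP 7.9.4 labels as device-related a column whose classes also include procedure-related events, so neither classification table isolates the device-related AE/SAE endpoint

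*SAP*

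**What the plan says.** SAP 5.3 lists "Device related AE and SAE's" among the safety endpoints, and Protocol 10.2.3 has the same endpoint. Neither mentions the procedure. Protocol 12.4 commits to summarising adverse events by, among other things, "relationship to study device and outcome".

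The class that fills the tables is wider than the endpoint. Protocol 14.1.2 states: "An ADE is an adverse event that, in the opinion of the Investigator, is related to the IP or the procedure". It counts possible, probable and definite relationships as related. SAP 7.4.4 states: "An ADE is defined as an Adverse Event that is Possibly or Probably Related to Device or Procedure".

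Protocol Table 14.1-1 heads the column holding these classes "DEVICE- OR PROCEDURE-RELATED". SAP 7.9.4 keeps the same ADE, ASADE and USADE cells in its event table and its patient table, but sets them against a column headed "NON DEVICE-RELATED" and names their own column as device-related only. SAP 7.11 records no change from the protocol's methods.

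For serious events, Protocol 14.1.4 requires a USADE to be caused by or related to the investigational product and not previously identified in the IFU. The remainder is then defined: "An Anticipated Serious Adverse Device Effect (ASADE) is a serious ADE that does not meet the criteria for a USADE".

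**The concern.** Every subject had surgery, so events attributed to the operation but not to the anchor can be expected to arise. Under the SAP's own ADE definition, such an event goes into a column that tells the reader it is device-related. Someone taking the device-related AE or SAE figure from either table would be reading a device-plus-procedure figure under a narrower label.

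Device safety is part of the stated primary objective, and the study exists to supply post-market evidence on this anchor. A heading that disagrees with the definition beneath it also leaves placement to whoever programs the table, so two programmers could produce different counts from the same data.

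**Working it through.** The plan gives no AE rate or expected count, so there is no figure to reproduce. The check traces where each kind of event lands.

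1. Event related to the device, rated possible or probable. It is an ADE in both documents and sits in the device-related column. Definition and heading agree.
2. Event related to the device, rated definite. It is an ADE under Protocol 14.1.2. Read literally, SAP 7.4.4 does not make it an ADE, because only the possible and probable levels are named.
3. Event related to the procedure only, rated possible or probable. By definition it is an ADE in both documents, so it enters the device-related column. By the heading alone it belongs in the other column, where the only class is one that the definitions exclude it from. Neither placement is consistent.
4. Serious event related to the procedure only and not identified in the IFU. It is a serious ADE. It cannot be a USADE, because Protocol 14.1.4 ties that class to the product. By default it is an ASADE, so it appears as anticipated in a column headed device-related.

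If the SAP definition decides placement, the accounting is:

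shown = D − F + P

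Here D is the true device-related count. F is the part of D rated definite for the device and not otherwise captured through a possible or probable procedure relationship. P is the procedure-only count rated possible or probable. The error is P − F: upward if P exceeds F, downward if F exceeds P, and zero if they are equal.

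To show the range, on assumed values only: let 2% of subjects have a device-related AE, 0% to 10% a procedure-only AE, and 0% to 50% of the device-related ones be rated definite. No subject has both kinds, and the ADE, ASADE and USADE cells are added together.

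- Lowest: 2% − (0.5 × 2%) + 0% = 1%.
- Highest: 2% − 0% + 10% = 12%.
- No procedure-only events and none rated definite: 2% − 0% + 0% = 2%, which is correct.

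These percentages show the mechanism and are not estimates for this study. If a subject can have both kinds of event, the subject-level excess is smaller than the procedure-only rate, because that subject is counted once.

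The data needed to separate the two exist. Protocol 14.2 has the investigator assess relationship to the device and to the procedure, and the SAP 7.9.4 listing drawn from the AE CRFs shows the two assessments separately.

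**The case against.** The strongest reply is that this is a labelling slip in a descriptive summary. Grouping device and procedure effects is the protocol's own convention, no test or threshold depends on the table, and the per-event listing lets anyone separate the two. Device-related re-intervention is tabulated separately, and Protocol 12.4 also promises a device-deficiency summary. The SAP says that table shells accompany it; they are not among the documents reviewed and might contain a device-only table.

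Much of that stands, and it rules out several stronger readings:

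- A reader might infer that the endpoint cannot be obtained at all, or that the device-safety conclusion would rest on this one number. The listing and the other device outcomes show otherwise. The endpoint is recoverable by hand, but not tabulated in the SAP text.
- A reader might infer that the device-related rate is necessarily overstated. That requires procedure-only events and requires the definition, not the heading, to decide placement. The omitted definite level works in the opposite direction.
- A reader might blame the SAP for the default into the anticipated cell. That rule comes from Protocol 14.1.4. The SAP also has an expectation item for serious ADEs and allows the AEMB to classify events, so some such events might be recorded differently.

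What the reply does not remove is the conflict between heading and definition in both tables. A listing is also not the summary that Protocol 12.4 promises.

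**Conclusion.** The point holds as a defect of definition and labelling. Neither SAP 7.9.4 classification table isolates device-related AEs and SAEs, and the SAP text specifies no other table that gives the promised summary by relationship to device. Followed as written, the device-related column includes any procedure-only events rated possible or probable, loses definite events if the SAP definition is read literally, and by default shows serious procedure-only events not in the IFU as anticipated device effects.

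The size and net direction are unknown without AE rates. The conclusion assumes that the ADE definition governs placement and that the unseen shells do not already make the split. The heading conflict itself depends on neither assumption. The primary endpoint and the sample size are unaffected. It should be corrected before the safety tables are produced, because it changes a reported figure for a named endpoint.

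**What to change.** - In both SAP 7.9.4 tables, restore the heading of Protocol Table 14.1-1 and split that column into device-related (with or without procedure) and procedure-related only, using the two existing CRF relatedness items.
- Report the device-related AE/SAE endpoint, as events and as subjects, from the first of these columns. This also delivers the Protocol 12.4 summary by relationship to device.
- Align the ADE definition in SAP 7.4.4 with the possible, probable and definite levels of Protocol 14.1.2.
- Show serious procedure-only events in their own cell and apply the anticipated/unanticipated split to device-related serious events only. Add a note that Protocol 14.1.4 would otherwise place the former under anticipated by default.

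The cost is SAP wording and two table shells. No new data are needed.
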